9.3 VARIABLES

9.3.1 Outcomes

For all three cohorts receiving empagliflozin, the following variables will be assessed:

9.3.1.1 Primary outcomes

- Previous occurrence (percentages) of
 - Typical CV comorbidities:
 - MI
 - Stroke
 - CAD
 - PAD
 - CHF (form (HFrEF/ HFpEF)

Proprietary confidential information © 2020 Boehringer Ingelheim International GmbH or one or more of its affiliated companies

- Other typical diabetes complications:
 - Neuropathy
 - Nephropathy / Renal function (eGFR, micro-/ macroalbuminuria)
 - Diabetic foot syndrome
 - Retinopathy (background and proliferative)
- Antidiabetic and cardiovascular co-medication (lipid-lowering agents, RAAS blockers, other antihypertensives, beta blockers, diuretics, antiplatelets and anticoagulants)

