Variables:	
For all three cohorts receiving empagliflozin, the baseline values of the following variables will be assessed:
 
 • Age (<65; 65 – <75; 75 – 80 , >80) • Gender • Weight [kg] • Height [cm] • HbA1c [% or mmol/ mol], FPG (available in subgroup only) • Previous occurrence of 
 ◦ Typical CV comorbidities: 
 ▪ MI ▪ Stroke ▪ CAD ▪ PAD ▪ CHF (form (HFrEF/ HFpEF) ◦ Other typical diabetes complications 
 ▪ Neuropathy ▪ Nephropathy / Renal function (eGFR, micro-/ macroalbuminuria) ▪ Diabetic foot syndrome ▪ Retinopathy (background and proliferative) • Antidiabetic and cardiovascular co-medication (lipid-lowering agents, RAAS blockers, other antihypertensives, beta blockers, diuretics, antiplatelets and anticoagulants) • Duration of diabetes (time since diagnosis) • Previous glucose-lowering treatment • Dosage of empagliflozin (10mg vs 25mg) (available in subgroup only) • Participation in Disease Management Programme (DMP) Type 2 Diabetes (from DPV registry) • Hospitalizations (from DPV registry)
Data sources:	
Data will be provided by the largest German T2D patient registries DPV& DIVE covering more than 500,000 patients.
 
The aim of the DPV initiative is to improve treatment outcomes in individuals with diabetes through standardized documentation and objective comparison of quality indicators as well as through multi-centre outcome research. Up to date, there are more than 400 centres participating in the initiative predominantly from Germany and from Austria.
 
DIVE is a national initiative for quality management of diabetes care. The aim is to transfer the already existing initiatives and software systems which collect patient-related data to a national diabetes registry. The DIVE registry is one of the biggest, most updated diabetes registries in Germany and part of the current development of a national diabetes registry. It is part of the first and second registry conference held by German Federal Ministry of Health (BMG) and Robert-Koch Institute (RKI).

Study size:	There will be about 7,900 patients on Empagliflozin included in the analysis.

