8. RESEARCH QUESTION AND OBJECTIVES

Description of the real-life treatment of adult patients with T2DM receiving empagliflozin, comparing the characteristics of patients starting Empagliflozin in three time intervals:

- The first analysis will include the patients receiving Empagliflozin before the EMPA-REG-OUTCOME study was published (time until mid-Sept. 2015; "Cohort 1").
- The second analysis will include patients receiving Empagliflozin starting from the EMPA-REG-OUTCOME study being published until CV Label Change (time from mid-Sept. 2015-mid-Jan. 2017; "Cohort 2").
- The third analysis will include all patients receiving Empagliflozin starting from mid-Jan. 2017 ("Cohort 3") until last available data cut.

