9.2 SETTING AND INCLUSION/EXCLUSION CRITERIA

Description of the real-life treatment of adult patients with T2DM receiving empagliflozin, comparing the characteristics of patients starting empagliflozin in three time intervals:

- The first analysis will include the patients receiving Empagliflozin before the EMPA-REG-OUTCOME study was published (time until mid-Sept. 2015; “Cohort 1”).
- The second analysis will include patients receiving Empagliflozin starting from the EMPA-REG-OUTCOME study being published until CV Label Change (time from mid-Sept. 2015-mid-Jan. 2017; “Cohort 2”).
- The third analysis will include all patients receiving Empagliflozin starting from mid-Jan. 2017 until last available data cut (“Cohort 3”).

Inclusion criteria:

- At least two outpatient T2DM diagnoses (ICD E11.-) in two different quarters and/or at least one inpatient T2DM diagnosis (ICD E11.-)
- At least one prescription of an empagliflozin-containing antidiabetic drug: Jardiance® (Empagliflozin, ATC A10BK03, former A10BX12) or Synjardy® (Empagliflozin/ Metformin, ATC A10BD20)

Exclusion criteria

- Any diagnosis of T1DM

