9.7 DATA ANALYSIS

9.7.1 Main analysis

Variables will be assessed in half-yearly periods after index date (date of first prescription of empagliflozin), for total study population and separated by study cohort.

Anonymized data from the DIVE and the DPV registries will be combined; nonparametric descriptive analyses will be used. Group comparison will be based on Wilcoxon rank sum test (continuous variables) and X²-test for binary/categorial values. Analysis will be implemented using SAS 9.4. Complete case analysis will be used.

Analysis will be done by an experienced biostatistician with detailed knowledge of the DIVE and the DPV registries. A second independent programmer will check the generated SAS code for inconsistencies. The medical team (

will evaluate the results from a clinical background to ensure plausibility.

Quality assurance and control will be the responsibility of the medical team (

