9.7.2 Missing data

In general, imputation of missing data will not be applied. In addition to that, no “Last observation carried forward” (LOCF) approach will be applied.

Implausible values will be set to missing values, as no correcting of values is possible due to the nature of the dataset. The defined lower and upper bounds for an acceptable range of continuous study variables are listed in Table 1; note that these ranges are defined with regards to obvious documentation mistakes.

Table 1: Lower and upper bounds for continuous study variables

Variable	Unit	Acceptable range
Age	Years	40 to 110
Prescriptions of CV or AD drugs per patient year	Number	1 to 300

In case of missing data for specific variables, reporting category “not reported/not available” will be used.

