5.1 Does the protocol describe how the study exposure is defined and measured? (e.g. operational details for defining and categorizing exposure, measurement of dose and duration of drug exposure)				-
5.2 Does the protocol address the validity of the exposure measurement? (e.g. precision, accuracy, use of validation sub-study)				-
5.3 Is exposure classified according to time windows? (e.g. current user, former user, non-use)				-
5.4 Is exposure classified based on biological mechanism of action and taking into account the pharmacokinetics and pharmacodynamics of the drug?				-

Comments:

As this is a cross-sectional study, there will be no follow-up period and thus no exposure measurement. A patient will be included after the first available record of drug use.

Section 6: Outcome definition and measurement	Yes	No	N/A	Section Number
6.1 Does the protocol specify the primary and secondary (if applicable) outcome(s) to be investigated?				9.3
6.2 Does the protocol describe how the outcomes are defined and measured?				9.3
6.3 Does the protocol address the validity of outcome measurement? (e.g. precision, accuracy, sensitivity, specificity, positive predictive value, prospective or retrospective ascertainment, use of validation sub-study)				9.8
6.4 Does the protocol describe specific endpoints relevant for Health Technology Assessment? (e.g. HrQoL, QALYs, DALYs, health care services utilization, burden of disease, disease management)				9.3

Comments:

--

Section 7: Bias	Yes	No	N/A	Section Number
7.1 Does the protocol describe how confounding will be addressed in the study?				

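### The primary outcome of previous comorbidity has no look-back rule, so unequal recorded history could create or mask a difference between the three cohorts

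*Combined protocol and SAP*

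**What the plan says.** The objective in section 8 is "comparing the characteristics of patients starting Empagliflozin in three time intervals". The first cohort is defined in section 9.2 by "time until mid-Sept. 2015", the second runs to mid-January 2017, and the third runs from then to the last data cut. The headline primary outcomes in section 9.3.1.1 are "Previous occurrence (percentages) of" MI, stroke, CAD, PAD, CHF and the listed diabetes complications. Section 9.7.1 plans chi-square tests for binary and categorical variables, with no adjustment.

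Three statements bear on when these variables are read, and they do not agree:

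- Section 4 (Abstract, Variables): "the baseline values of the following variables will be assessed".
- Section 9.7.1: "Variables will be assessed in half-yearly periods after index date (date of first prescription of empagliflozin").
- Annex 2, comment under checklist section 5: "As this is a cross-sectional study, there will be no follow-up period and thus no exposure measurement". The same comment gives the entry rule: "A patient will be included after the first available record of drug use".

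No section gives a look-back length, a minimum time in the registry before the index date, or an ever-recorded rule. Checklist item 7.2.2, which names time-related bias, is marked not applicable. Item 12.1.2 ticks information bias as discussed, but sections 9.9 and 9.11 cover only non-randomised treatment and the difference between registry and non-registry patients.

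**The concern.** A patient counts as having a previous MI only if the registry holds a record of it. The longer a patient has been documented before the index date, the more chances there have been for an old condition to be entered. The cohorts are defined by calendar time. For two patients who entered a registry on the same day, one starting in Cohort 3 has at least 16 months more documentation before the index date than one starting in Cohort 1 (mid-September 2015 to mid-January 2017).

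If that pattern holds on average, recorded cardiovascular disease would rise across cohorts without any change in who is given the drug. A rise is also what a real shift in prescribing after the outcome trial and the label change would produce. As planned, nothing in the output would separate the two, and this is the study's central comparison.

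**Working it through.** **No figure to reproduce.** The plan gives about 7,900 patients in total (section 9.5), with no split by cohort, no prevalence and no significance level. What follows is an illustration.

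**Inputs from the protocol.** The cohort boundaries (mid-September 2015, mid-January 2017) and N = 7,900.

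**Assumptions.** True prevalence P = 30% in every cohort; registry entry uniform from 2010 to the start date; Cohort 1 starts within the year before mid-September 2015; data cut 1 September 2019; a share *a* of conditions recorded at entry and the rest at rate *r* per year; two-sided 5% tests of Cohort 1 against Cohort 3.

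**Step 1, mean history.** Half the distance from 2010 to the mean start date:

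- Cohort 1: (2015.21 − 2010)/2 = 2.6 years
- Cohort 2: (2016.38 − 2010)/2 = 3.2 years
- Cohort 3: (2018.35 − 2010)/2 = 4.2 years

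**Step 2, recorded prevalence.** P × [1 − (1 − a) × M], where M is the cohort mean of exp(−rL) and L is years of history. For Cohorts 1, 2 and 3, M is 0.694, 0.644, 0.571 at r = 0.15 and 0.506, 0.446, 0.368 at r = 0.30. The false rise from Cohort 1 to Cohort 3 is 0.30 × (1 − a) × (M1 − M3):

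| a | r = 0.15 | r = 0.30 |
|---|---|---|
| 50% | 0.30 × 0.5 × 0.123 = 1.8 points | 0.30 × 0.5 × 0.138 = 2.1 points |
| 70% | 1.1 points | 1.2 points |
| 90% | 0.4 points | 0.4 points |

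**Step 3, scale.** With three equal cohorts of 2,633, a difference reaches p < 0.05 at 1.96 × √(2p(1 − p)/2633). That is 2.2 to 2.4 points for the recorded prevalences above (20% to 29%). With a 10/30/60% split it is about 3.1 to 3.4 points. No cell in the table reaches the threshold by itself, but a shift below it still inflates the false-positive rate. At 2.1 points the standard error is 2.29/1.96 = 1.17 points, so the chance of a significant result is about Φ(2.07/1.17 − 1.96) = 0.42. The same calculation gives about 0.18 at 1.2 points and 0.06 at 0.4 points, against a nominal 0.05.

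**Step 4, sensitivity to the history assumption.** Give every patient in a cohort the same history, with P = 30%, a = 50%, r = 0.20:

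- 2, 3 and 4.5 years: 19.9%, 21.8%, 23.9%, a false rise of 4.0 points
- 2 years in all cohorts: no difference
- 4.5, 3 and 2 years: a false fall of 4.0 points

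**Step 5, does stratifying remove it?** Among patients with, say, 2.5 years of history (a = 70%, r = 0.15), recorded prevalence is 0.30 × (1 − 0.30 × exp(−0.375)) = 23.8% whatever the cohort.

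**Step 6, would a short fixed window do as well?** Suppose lasting conditions are entered once only. Restrict to patients with at least 12 months of history and count records from the last 12 months only. The same model gives 0.93% in Cohort 1 and 0.76% in Cohort 3 (a = 70%, r = 0.15), or 2.21% and 1.57% (a = 50%, r = 0.30). Nearly all true cases are lost and a false decline appears.

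**The case against.** The strongest objection is that direction is assumed. The 16-month gap applies to two patients with the same entry date, and the protocol says nothing about when patients enter the registries. If patients typically join close to starting the drug, or the registries keep taking in new patients and centres, history length need not differ by cohort and the artefact vanishes. This stands: a reader might infer that later cohorts have more history by construction, and the documents do not support that.

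The sign could also reverse. If section 9.7.1 governs and conditions are gathered over all time after the index date, earlier cohorts have had longer to accumulate records. With an assumed cut on 1 September 2019, that is at least 47.5 months for Cohort 1 and at most 31.5 months for Cohort 3. This stands too, and it makes reconciling the assessment time the first step.

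A reader might further infer that the ban on carrying observations forward in section 9.7.2 would erase an MI recorded in an earlier period. It would not: that section deals with missing values, and a documented MI is an observed history.

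Finally, the study is descriptive, the checklist records no prior hypothesis, and the illustrative artefact is modest. That limits the seriousness of the point. But the protocol does plan formal comparisons of these percentages, and the general cautions in sections 9.9 and 9.11 do not mention unequal history.

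**Conclusion.** The omission is a matter of fact: the headline primary outcomes have no look-back rule, no minimum registry time and no check on history length, and they are compared unadjusted across calendar cohorts. The consequence is a possibility, not a demonstrated bias. The false rise from Cohort 1 to Cohort 3 is about 0.4 to 2.1 points under the uniform-entry assumptions, up to 4.0 points if history more than doubles and only half of conditions are recorded at entry, and zero if history is equal. It could be negative. Only N and the cohort boundaries come from the protocol. The point should be addressed before analysis because the check is cheap and the comparison affected is the main one.

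**What to change.** 1. Define previous occurrence as any record up to and including the index date. Reconcile this with the post-index assessment in section 9.7.1 and the no-follow-up comment in Annex 2.
2. Tabulate time from first registry record to index date, by cohort and by registry.
3. Add a sensitivity analysis that repeats the primary comorbidity and complication comparisons stratified by, or adjusted for, length of history before the index date.
4. State that a cohort difference will be interpreted with caution as a change in patient profile if it shrinks materially in that analysis.

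A fixed 12-month look-back should not be used as the check, for the reason in step 6 of the working. Nor should a difference be reported only if it survives such a check, since that could hide a real shift.

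The cost is some wording, one extra table and one repeat analysis. The strata will be smaller and their estimates less precise.

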9.3.1.2 Secondary outcomes

- Age (<65; 65 – <75; 75 – 80 , >80)
- Gender
- Weight [kg]
- Height [cm]
- HbA1c [% or mmol/ mol], FPG (available in subgroup only)
- Duration of diabetes (time since diagnosis)
- Previous glucose-lowering treatment
- Dosage of empagliflozin (10mg vs 25mg) (available in subgroup only)
- Participation in Disease Management Programme (DMP) Type 2 Diabetes (from DPV registry)
- Hospitalizations (from DPV registry)

9.4 DATA SOURCES

Data will be provided by the largest German T2D patient registries DPV& DIVE covering more than 500,000 patients.

The aim of the DPV initiative is to improve treatment outcomes in individuals with diabetes through standardized documentation and objective comparison of quality indicators as well as through multi-centre outcome research. Up to date, there are more than 400 centres participating in the initiative predominantly from Germany and from Austria.

DIVE is a national initiative for quality management of diabetes care. The aim is to transfer the already existing initiatives and software systems which collect patient-related data to a national diabetes registry. The DIVE registry is one of the biggest, most updated diabetes registries in Germany and part of the current development of a national diabetes registry. It is part of the first and second registry conference held by German Federal Ministry of Health (BMG) and Robert-Koch Institute (RKI).

9.5 STUDY SIZE

There will be about 7,900 patients on Empagliflozin included in the analysis.

9.6 DATA MAIN MANAGEMENT

The medical team (

will be responsible for data management, including quality checking of the data. It is pointed out that no individual patient data will be used in this study and that data will only be presented in aggregated form.

9.7 DATA ANALYSIS

9.7.1 Main analysis

Variables will be assessed in half-yearly periods after index date (date of first prescription of empagliflozin), for total study population and separated by study cohort.

Anonymized data from the DIVE and the DPV registries will be combined; nonparametric descriptive analyses will be used. Group comparison will be based on Wilcoxon rank sum test (continuous variables) and X²-test for binary/categorial values. Analysis will be implemented using SAS 9.4. Complete case analysis will be used.

Analysis will be done by an experienced biostatistician with detailed knowledge of the DIVE and the DPV registries. A second independent programmer will check the generated SAS code for inconsistencies. The medical team (

will evaluate the results from a clinical background to ensure plausibility.

Quality assurance and control will be the responsibility of the medical team (

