Research question and objectives:	
Description of the real-life treatment of adult patients with T2DM receiving empagliflozin, comparing the characteristics of patients starting empagliflozin in three time intervals:
 
 - The first analysis will include the patients receiving Empagliflozin before the EMPA-REG-OUTCOME study was published (time until mid-Sept. 2015; "Cohort 1"). - The second analysis will include patients receiving Empagliflozin starting from the EMPA-REG-OUTCOME study being published until CV Label Change (time from mid-Sept. 2015-mid-Jan. 2017; "Cohort 2"). - The third analysis will include all patients receiving Empagliflozin starting from mid-Jan. 2017 until last available data cut ("Cohort 3").
Study design:	
Retrospective non-interventional cross-sectional study using real-world data from German patient registries. Data will be provided by the largest German T2D patient registries DPV& DIVE covering more than 500,000 patients.

Population:	
Inclusion criteria:
 
 • Adult patients with at least two outpatient T2DM diagnoses (ICD E11.-) in two different quarters and/or at least one inpatient T2DM diagnosis (ICD E11.-) – AND – • At least one prescription of an empagliflozin-containing antidiabetic drug: Jardiance® (Empagliflozin, ATC A10BK03, former

	A10BX12) or Synjardy® (Empagliflozin/Metformin, ATC A10BD20)
--	---

Exclusion criteria

- Any diagnosis of T1DM.

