9.10 SUBJECTS

All patients with T2DM from the DPV & DIVE registries receiving Empagliflozin will be included. The patients will be divided in three cohorts based on the time point of Empagliflozin treatment start to better identify the differences between these cohorts.

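### The main analysis assesses variables by half-year after the first empagliflozin prescription, while the abstract and design describe a cross-sectional baseline study; the time point of the cohort comparison is never stated

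*Combined protocol and SAP*

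**What the plan says.** Section 9.7.1 (Main analysis) opens with "Variables will be assessed in half-yearly periods after index date (date of first prescription of empagliflozin", for the total population and by cohort. The Data analysis row of the abstract (section 4) repeats the sentence. The next paragraph of 9.7.1 names the Wilcoxon rank sum test for continuous variables and the chi-square test for binary and categorical ones. It gives no time point for either.

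Other parts describe one assessment at the start of treatment:
- The Variables row of the abstract says "the baseline values of the following variables will be assessed".
- The abstract and section 9.1 give the design as "Retrospective non-interventional cross-sectional study using real-world data from German patient registries".
- Section 8 sets the objective as "comparing the characteristics of patients starting Empagliflozin in three time intervals".
- The comment to section 5 of the ENCePP checklist (Annex 2) says "As this is a cross-sectional study, there will be no follow-up period and thus no exposure measurement".

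Section 9.3.1, which introduces the primary and secondary outcomes, does not settle the matter. It says only "For all three cohorts receiving empagliflozin, the following variables will be assessed" and drops the word baseline. Section 9.3.1.1 words the comorbidity and complication outcomes as "Previous occurrence (percentages) of" each condition. No section defines baseline or gives a window around the index date.

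**The concern.** The study asks whether the patients put on empagliflozin differed across three calendar intervals. That needs their characteristics at the start of treatment. A programmer who follows 9.7.1 would tabulate values after the start; one who follows the abstract's Variables row would tabulate baseline values. Both could claim to follow the plan, and the second programmer who checks the code has no single specification to check against.

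The choice matters most for variables that can change on treatment. Two of them, co-medication and renal function, are primary outcomes. If they are read after the start, a difference between cohorts no longer answers the question in section 8. Leaving the time point open also allows it to be chosen after the results are seen.

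**Working it through.** The plan gives no figure to reproduce on this point, so the check compares the text and adds one piece of date arithmetic.

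**Step 1. The statements side by side.**

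| Place | Timing implied |
|---|---|
| 9.7.1; abstract, Data analysis | Repeated half-years after each patient's first prescription |
| Abstract, Variables | Baseline |
| Abstract, Study design; 9.1 | Cross-sectional |
| Section 8 | Characteristics of patients starting the drug |
| Annex 2, checklist section 5 comment | No follow-up |
| Abstract, Rationale; section 7 | Interest in outcomes associated with treatment |
| 9.7.2, Table 1 | A plausibility range for prescriptions per patient-year, a person-time measure |
| Annex 2, item 4.2.5 | Duration of follow-up ticked Yes with reference to 9.2, which gives none |

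Rows 2 to 5 conflict with row 1. The last three rows suggest that some description after the index date may be intended. Section 5 records no amendments and Annex 1 lists no stand-alone document, so nothing else resolves the conflict.

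**Step 2. What the choice changes.** For a time-varying variable, write the value in half-year k for cohort c as B(c) + D(c,k), where B is the value at start and D the change since then. The contrast of Cohorts 1 and 3 in half-year k is

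[B(1) − B(3)] + [D(1,k) − D(3,k)].

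The objective concerns the first bracket only. If D is the same in all cohorts, the second bracket is zero and the contrast survives, but the values still misdescribe patients at start. If D differs between cohorts, the difference appears as one in who was started. The variables concerned are co-medication and renal function (9.3.1.1) and HbA1c, FPG, weight and hospitalizations (9.3.1.2). Sex and height are unaffected. The documents give no value for D, so the second bracket cannot be sized.

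**Step 3. Availability of later half-years.** Inputs: cohort boundaries of mid-September 2015 and mid-January 2017 (section 8), taken as the 15th. The data cut is not given. The abstract's start of data access, 1 September 2019, is used as an assumption, with 1 January 2019 and 31 October 2019 as a range. Complete half-years = whole part of (months from boundary to cut ÷ 6).

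| Assumed cut | From Cohort 1/2 boundary | From Cohort 2/3 boundary |
|---|---|---|
| 1 Jan 2019 | 39.6 months, 6 half-years | 23.5 months, 3 half-years |
| 1 Sep 2019 | 47.5 months, 7 half-years | 31.5 months, 5 half-years |
| 31 Oct 2019 | 49.5 months, 8 half-years | 33.5 months, 5 half-years |

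With the 1 September 2019 cut, the calendar leaves room for at least 7 complete half-years for every Cohort 1 patient, about 5 to 7 in Cohort 2, and 0 to 5 in Cohort 3. Complete case analysis without imputation (9.7.1, 9.7.2) does not even this out. A baseline comparison does not depend on it.

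**The case against.** The strongest reply is that the half-yearly sentence and the sentence on group comparison stand in separate paragraphs of 9.7.1. The first may be purely descriptive, with the tests run on baseline values. That is possible, and it stands as a limit: the documents do not show that post-index values will enter the tests. They do not show the opposite either, because no section labels the half-yearly output as additional and it opens the main analysis without restriction.

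A second reply is that baseline is plainly meant and the sentence is a slip printed twice. The documents do not support that certainty. The rationale speaks of outcomes associated with treatment, Table 1 bounds a rate per patient-year, and the first clause of the objective concerns real-life treatment. Some post-index description may be deliberate. What stands is that the request should be to reconcile the text and to allow such an analysis under its own label.

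Reading the half-years as calendar periods does not help, since the sentence ties them to each patient's index date.

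Some stronger readings should also be set aside. Section 9.10 says "The patients will be divided in three cohorts based on the time point of Empagliflozin treatment start". A reader might count this as a further contradiction, but it only allocates patients to cohorts and fits any assessment time. A reader might also want the bias expressed as percentage points needed for significance. That would require a significance level, cohort sizes and a pairwise contrast, none of which the plan states, and it would describe the test and not this problem. Finally, a reader might infer a definite false gap in comorbidity history from unequal observation time, or conclude that it is negligible. Either depends on incidence, on the half-year compared and on the handling of patients who do not reach it, and the documents give none of these.

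**Conclusion.** The point holds as an inconsistency in the current text and should be fixed. The half-yearly post-index rule conflicts with the baseline wording, the cross-sectional design and the statement of no follow-up, and it does not fit an objective about patients starting the drug. The time point of the cohort comparison is stated nowhere.

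Confidence is high for the contradiction. The consequence is conditional: only if the half-yearly rule governs the comparison do the time-varying variables become on-treatment values, mixing selection at start with later change. No size can be derived and none is claimed. The half-year counts illustrate unequal calendar availability only; they rest on the assumed data cuts and on reading mid-month as the 15th, and they say nothing about how many patients remain documented.

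**What to change.** In 9.7.1, 9.3.1 and the abstract, state that the cohort comparison of patient characteristics uses one baseline assessment per patient relative to the index date. It should use one pre-specified window, identical for all cohorts, whose position and length the sponsor sets.

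Then either delete the half-yearly sentence in both places, or keep it as a separately labelled descriptive post-index analysis. If kept, it should show the number of patients available per half-year and cohort, and it should not be used for the comparison of starters. Align checklist item 4.2.5 and the comment to checklist section 5 with the choice.

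The cost is mainly wording. Some patients will have no value in the window and will fall into the not-reported category of 9.7.2 for that variable. How many cannot be judged from the documents, which do not say how much data the registries hold before the index date.
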